### **3.2 Secondary Objective(s) & Hypothesis(es)**

#### **MDS (Cohort 1)**

- 1) **Objective:** To evaluate the OS in subjects with intermediate-1, intermediate-2, or high risk MDS whose disease has failed to respond to at least 4 cycles of a HMA.
- 2) **Objective:** To evaluate Bone Marrow Response in subjects with intermediate-1, intermediate-2, or high risk MDS whose disease has failed to respond to at least 4 cycles of a HMA.
- 3) **Objective:** To evaluate Hematologic Improvement based on IWG criteria for MDS in subjects with intermediate-1, intermediate-2, or high risk MDS whose disease has failed to respond to at least 4 cycles of a HMA.
- 4) **Objective:** To evaluate Cytogenetic Response based on IWG criteria for MDS in subjects with intermediate-1, intermediate-2, or high risk MDS whose disease has failed to respond to at least 4 cycles of a HMA.
- 5) **Objective:** To evaluate Duration of Response (DOR) in subjects with intermediate-1, intermediate-2, or high risk MDS whose disease has failed to respond to at least 4 cycles of a HMA.
- 6) **Objective:** To compare in bone marrow biopsies the extent of pre- pembrolizumab PD-L1 expression and change in PD-L1 expression after treatment with a HMA for pembrolizumab responders versus non-responders in subjects with intermediate-1, intermediate-2, or high risk MDS whose disease has failed to respond to at least 4 cycles of a HMA.

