o. In subjects who discontinue study therapy without confirmed disease progression, a response assessment should be performed at the time of treatment discontinuation (i.e. date of discontinuation ± 4 week window). If previous assessment was performed within 4 weeks prior to the date of discontinuation, then a repeat assessment at treatment discontinuation is not mandatory. p. For women of reproductive potential, a urine pregnancy test should be performed within 72 hours prior to first dose of trial treatment. If urine pregnancy results cannot be confirmed as negative, a serum pregnancy test performed by the local study site laboratory will be required. Pregnancy tests (serum and/or urine tests) should be repeated if required by local guidelines. q. Coagulation factors (PT/INR and aPTT) should be tested as part of the screening procedures for all subjects. Any subject receiving anticoagulant therapy should have coagulation factors monitored closely throughout the trial. r. Laboratory tests for screening are to be performed within 7 days prior to the first dose of trial treatment. See Section 7.1.3 for details regarding laboratory tests. s. After Cycle 1, laboratory samples can be collected up to 72 hours prior to the scheduled time point. See Section 7.1.3 for details regarding laboratory tests. t. Unresolved abnormal laboratory tests that are drug related AEs should be followed until resolution. Laboratory tests do not need to be repeated after the end of treatment if laboratory tests are within normal range. u. To be repeated every 4 cycles after Cycle 5. v. To be repeated every 3 cycles after cycle 7. w. Detailed instructions for bone marrow collection, processing and shipment are provided in the Procedures Manual. Bone marrow biopsy and aspirate should be collected at screening, Wk 6 (± 7 days), Wk 12 (± 7 days), and every 12 weeks while on study treatment or as clinically indicated. If a subject has disease progression at Wk 12 and a confirmatory assessment is performed at Wk 16, a biopsy and aspirate should be performed as part of the confirmation assessment. A confirmation biopsy does not need to be performed for subjects who have stable disease, partial response, or complete response at Wk 12. x. If the subject signs the Future Biomedical Research (FBR) consent, any leftover tissue that would ordinarily be discarded at the end of the main study will be retained for FBR. y. Bone marrow morphology, Blast percentage, and Cytogenetics should be performed with each bone marrow biopsy/aspirate procedure. Iron stain is performed at screening only. Cytogenetics is done to evaluate whether genetic variation within a clinical trial population correlates with response to the treatment(s) under evaluation. If it is not a standard procedure in your region, this test does not need to be performed. z. If available, bone marrow biopsies will be collected from pre and post HMA treatment. aa. Correlative study samples should be collected at Screening, at the time of the Wk 6/Wk 12 disease response assessments, and upon progression.													

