Secondary binary endpoints 
 
• MDS (Cohort 1):                     
 
a. Bone marrow response by IWG criteria (investigator assessed)
 
b. Hematologic improvement by IWG criteria (investigator-assessed)
 
c. Cytogenetic response by IWG criteria (investigator assessed)
 
 
 
• MM (Cohort 2):                     
 
a. CR + sCR by IMWG criteria (investigator assessed)
 
 
 
• HL (Cohort 3):                     
 
a. ORR
 
 
 
• NHL monotherapy (Cohort 4): none
 
• NHL combination therapy (Cohort 5): none
 
	Exact test of binomial parameter	FAS	Subjects with missing data are considered non-responders

Endpoint/Variable (Description, Time Point)	Statistical Method	Analysis Population	Missing Data Approach
Secondary time-to-event endpoints 1. MDS (Cohort 1): a. OS b. DOR 2. MM (Cohort 2): a. TTP b. DOR c. PFS d. OS 3. HL (Cohort 3): a. PFS b. OS c. DOR 4. NHL monotherapy (Cohort 4): a. PFS b. OS c. DOR 5. NHL combination therapy (Cohort 5): a. PFS b. OS c. DOR	Summary statistics using Kaplan-Meier method	OS, TTP, PFS: FAS DOR: all responders	Censored at last assessment
Secondary descriptive analyses Response by PD-L1 expression change before and after HMA treatment in each population separately: 1. MDS (Cohort 1) 2. MM (Cohort 2) 3. HL (Cohort 3) 4. NHL monotherapy (Cohort 4) 5. NHL combination therapy (Cohort 5)	Descriptive statistics	FAS	

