#### **MDS (Cohort 1)**

The primary efficacy endpoint for the MDS cohort is ORR, defined as the proportion of subjects in the analysis population who have response according to the IWG 2006 criteria at any time during the study. Response for the primary analysis will be determined by the investigator.

Key secondary efficacy endpoints for the MDS cohort include:

- OS
- Bone Marrow Response based on IWG criteria for MDS (investigator-assessed)
- Hematologic improvement based on IWG criteria for MDS (investigator-assessed)
- Cytogenetic response based on IWG criteria for MDS (investigator-assessed)
- DOR
- Response by PD-L1 expression change before and after HMA treatment

Additional analyses of efficacy endpoints in MDS based on central review of bone marrow assessment may be conducted at the end of the trial and will be considered exploratory.

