## 12.7 Disease Response Criteria

### 12.7.1 MDS Disease Response Criteria

Cheson et al. Clinical application and proposal for modification of the International Working Group (IWG) response criteria in myelodysplasia. *Blood*. 2006; 108:419-425.

Criteria for MDS disease assessment:

Table 3. Proposed modified International Working Group response criteria for altering natural history of MDS

Category	Response criteria (responses must last at least 4 wk)
Complete remission	Bone marrow: < 5% myeloblasts with normal maturation of all cell lines* Persistent dysplasia will be noted† Peripheral blood‡ Hgb > 11 g/dL Platelets > 100 x 10  /L Neutrophils > 1.0 x 10  /L† Blasts 0%
Partial remission	All CR criteria if abnormal before treatment except: Bone marrow blasts decreased by > 50% over pretreatment but still > 5% Cellularity and morphology not relevant
Marrow CR†	Bone marrow: < 5% myeloblasts and decrease by > 50% over pretreatment† Peripheral blood: if HI responses, they will be noted in addition to marrow CR†
Stable disease	Failure to achieve at least PR, but no evidence of progression for > 8 wks
Failure	Death during treatment or disease progression characterized by worsening of cytopenias, increase in percentage of bone marrow blasts, or progression to a more advanced MDS FAB subtype than pretreatment
Relapse after CR or PR	At least 1 of the following: Return to pretreatment bone marrow blast percentage Decrement of > 50% from maximum remission/response levels in granulocytes or platelets Reduction in Hgb concentration by > 1.5 g/dL or transfusion dependence
Cytogenetic response	Complete Disappearance of the chromosomal abnormality without appearance of new ones Partial At least 50% reduction of the chromosomal abnormality
Disease progression	For patients with: Less than 5% blasts: > 50% increase in blasts to > 5% blasts 5%-10% blasts: > 50% increase to > 10% blasts 10%-20% blasts: > 50% increase to > 20% blasts 20%-30% blasts: > 50% increase to > 30% blasts Any of the following: At least 50% decrement from maximum remission/response in granulocytes or platelets Reduction in Hgb by > 2 g/dL Transfusion dependence
Survival	Endpoints: Overall: death from any cause Event free: failure or death from any cause PFS: disease progression or death from MDS DFS: time to relapse Cause-specific death: death related to MDS

Deletions to IWG response criteria are not shown.

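### In the MDS cohort the plan lets sites skip cytogenetics yet scores a missing result as non-response, so the cytogenetic response rate is understated if any subject goes untested.

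*Combined protocol and SAP*

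**What the plan says.** Section 6.1, Chart A, footnote y starts from a requirement: "Bone marrow morphology, Blast percentage, and Cytogenetics should be performed with each bone marrow biopsy/aspirate procedure". It gives a correlative purpose, "Cytogenetics is done to evaluate whether genetic variation within a clinical trial population correlates with response to the treatment(s) under evaluation", and then waives the test: "If it is not a standard procedure in your region, this test does not need to be performed". Chart G (Section 6.7, Cohort 1 second course) repeats the waiver in footnote w.

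Section 3.2 lists a Cohort 1 secondary objective that needs this test: "To evaluate Cytogenetic Response based on IWG criteria for MDS". Section 8.2.3.1 names it as a key secondary endpoint, assessed by the investigator. Tables 15 and 17 place it among the secondary binary endpoints, with an exact binomial test and this missing-data rule: "Subjects with missing data are considered non-responders". The primary population is the FAS, and Table 17 adds ITT as supportive.

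Section 8.2.4.1 admits a subject to the FAS on three conditions: at least one dose, a baseline disease assessment, and either a post-baseline disease assessment or discontinuation for progression or a drug-related adverse event. A karyotype is not among them.

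The criteria reproduced in Section 12.7.1 define complete cytogenetic response as "Disappearance of the chromosomal abnormality without appearance of new ones", and partial response as a reduction of the abnormality by at least half.

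**The concern.** Both parts of the response definition compare a later karyotype with an abnormal earlier one, so a subject who is never karyotyped cannot be a responder. Such a subject still enters the FAS and is counted as a non-responder.

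Scoring missing data as failure is usually defended because missingness may itself signal failure, as in early dropout. That reasoning does not cover a test left undone because it is not routine in the region, which the protocol expressly allows. The reported rate would then partly reflect local laboratory practice.

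The waiver sits oddly in this cohort. The lymphoma charts carry the same sentence (for example Chart C footnote aa and Chart E footnote bb), but no lymphoma endpoint depends on cytogenetics. In Cohort 1 one does. At stake is how a stated secondary objective is read in a cohort of about 25, where a few untested subjects move the rate visibly.

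**Working it through.** **Inputs.** From Sections 8.1.3 and 8.2.7: Cohort 1 has about 25 subjects, null ORR 10%, alternative 30%, one-sided 5%, and success at 6 of 25 or more. The documents give no expected rate and no null rate for cytogenetic response, and no count of untested subjects. Both the rate and the count below are assumed and shown over a range.

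**The plan's own figure.** With X binomial, n = 25:
- P(X ≥ 6 | 0.10) = 0.0334
- P(X ≥ 5 | 0.10) = 0.0980, so 6 is the smallest count that meets 5%
- P(X ≥ 6 | 0.30) = 0.8065

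The stated power of about 80% is reproduced. It concerns ORR and is used here only to fix the denominator of 25.

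**Dilution.** Let p be the rate that would be seen if all 25 were tested, and u the number untested. Assume untested subjects would respond at the same rate as tested ones. Then:

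expected reported rate = p × (25 − u) / 25

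| p | u = 0 | u = 3 | u = 5 | u = 8 | u = 10 |
|---|---|---|---|---|---|
| 30% | 30.0% | 26.4% | 24.0% | 20.4% | 18.0% |

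For example, 0.30 × 20/25 = 0.24 and 0.30 × 15/25 = 0.18. At p = 20% the rates for u = 5 and u = 10 are 16.0% and 12.0%. At p = 40% they are 32.0% and 24.0%. The relative loss is u/25 whatever the value of p: 20% for five untested and 40% for ten.

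**The same in counts.** Suppose six responders are observed. The intervals are exact 90% (Clopper-Pearson), computed here only to show what a smaller denominator costs.

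| Denominator | Rate | 90% interval | Width |
|---|---|---|---|
| FAS, 25 | 24.0% | 11.0 to 42.0% | 31.0 points |
| Tested, 20 (5 untested) | 30.0% | 14.0 to 50.8% | 36.8 points |
| Tested, 15 (10 untested) | 40.0% | 19.1 to 64.0% | 44.9 points |

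**A related gap.** No rule covers subjects whose baseline karyotype is normal. They have no abnormality to lose, so they cannot meet the Section 12.7.1 definition either. A denominator of all tested subjects would still include them.

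**The case against.** The strongest reply is that the effect may be nil. Nothing in the documents says that any site or subject went untested, and if all were tested the rate is unaffected. That stands, so the bias must be stated conditionally.

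It can also be said that missing-as-failure is conventional, works against the drug, and here touches one of several secondary endpoints. Section 8.2.6 controls error for the primary endpoint only, and Section 8.2.5 treats other efficacy p-values as nominal. This limits the importance of the point. It does not remove the mismatch between an optional test and a rule that scores its absence as failure.

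Three stronger readings are tempting, and the documents do not support them:

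- *The primary ORR is also understated.* A reader might infer this because Section 12.7.1 lists cytogenetic response in the same table as remission. The SAP does not say which categories count toward ORR, so no effect on ORR or on the 6-of-25 rule can be shown.
- *Eligibility and the IPSS analyses are undermined.* That depends on what IPSS contains, which the documents do not list. If it did include karyotype, the IPSS scores required at entry and in Chart A would push sites to test, at least at baseline.
- *A planned confidence interval is wrong.* Section 8.2.5.1 promises the 90% interval for the primary endpoint. For secondary binary endpoints, Tables 15 and 17 list only the exact test.

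Finally, deleting the waiver may look like the obvious remedy. The Document History entry for Amendment 04 records Cohort 1 enrolment as complete, so deletion cannot recover karyotypes that were never taken.

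**Conclusion.** The point holds in conditional form. If any Cohort 1 subject is untested under the waiver, the planned analysis counts that subject as a cytogenetic failure and the reported rate is too low. The relative understatement equals the untested share, on the assumption that untested subjects would have responded like tested ones. The falls from 30% to 24% or 18% are illustrations at assumed counts of 5 and 10 of 25, not estimates for this trial. The finding is confined to one secondary endpoint, and the ORR power calculation stands. It is still worth acting on. Section 8.1 leaves room for changes reported in the study report for Cohorts 2 and 5 only, so the Cohort 1 rule applies as written unless the plan is changed.

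**What to change.** In Tables 15 and 17, for cytogenetic response only:

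1. Make the main estimate the rate among FAS subjects with an abnormal baseline karyotype and at least one post-baseline karyotype.
2. Keep the FAS rate, with missing counted as non-response, as a supportive estimate.
3. Report the numbers untested at baseline, normal at baseline, and without a post-baseline karyotype.

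This needs no new procedure. The cost is a smaller denominator and a wider interval, as the second table in the working shows. The main estimate also leaves out subjects who stopped before a later marrow, some of whom may be genuine failures. The supportive FAS rate and the reported counts keep that visible. Removing the waiver for any Cohort 1 marrows still to be taken under Charts A or G is optional. It would add a test at sites that do not run it routinely, and the fix does not depend on it.

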## 6.2 Study Flow Chart B: Cohort 2-Multiple Myeloma (Subjects allocated to 10mg/kg Q2W)

Trial Period:	Screening Phase	Treatment Cycles a								End of Treatment	Post-treatment		
		To be repeated beyond 8 cycles											
Treatment Cycle/Title:	Screening (Visit 1)	1	2	3	4	5	6	7	8	Discon	Post-Treatment Safety Follow-up Visit	Efficacy Follow-up Visits b	Survival Follow-up c
	Scheduling Window (Days) d :	-28 to -1	± 3	± 3	± 3	± 3	± 3	± 3	± 3	At time of Discon	30 days post Discon (±3 days)	Every 12 weeks post Discon (±7 days)	Every 12 weeks (±7 days) or as directed by the Sponsor
Administrative Procedures													
Informed Consent	X e												
Informed Consent for Future Biomedical Research	X f												
Inclusion/Exclusion Criteria	X												
Subject Identification Card	X												
Demographics and Medical History	X												
Prior and Concomitant Medication Review g	X	X	X	X	X	X	X	X	X	X			
International Staging System Criteria h	X												
Trial Treatment Administration		X	X	X	X	X	X	X	X				
Post-study anticancer therapy status											X	X	
Survival Status												X	
Clinical Procedures/Assessments													
Review Adverse Events i	X	X	X	X	X	X	X	X	X	X	X j	X j	
Full Physical Examination	X						X k			X			
Directed Physical Examination		X			X			X					
Vital Signs and Weight l	X	X	X	X	X	X	X	X	X	X			
12-Lead Electrocardiogram	X												
ECOG Performance Status	X	X	X	X	X	X	X	X	X	X			
Skeletal survey m	X												
MRI/CT/PET m	X												

Trial Period:	Screening Phase	Treatment Cycles a								End of Treatment	Post-treatment		
		To be repeated beyond 8 cycles											
Treatment Cycle/Title:	Screening (Visit 1)	1	2	3	4	5	6	7	8	Discon	Post-Treatment Safety Follow-up Visit	Efficacy Follow-up Visits b	Survival Follow-up c
Scheduling Window (Days) d :	-28 to -1	± 3	± 3	± 3	± 3	± 3	± 3	± 3	± 3	At time of Discon	30 days post Discon (±3 days)	Every 12 weeks post Discon (±7 days)	Every 12 weeks (±7 days) or as directed by the Sponsor
International Myeloma Working Group Uniform Response Criteria n				X		X		X o		X p		X b	
Laboratory Procedures/Assessments: analysis performed by local laboratory													
Pregnancy Test – Urine or Serum β-HCG q	X												
PT/INR and aPTT r	X s												
CBC with Differential t	X s			X		X		X		X		X u	
Comprehensive Chemistry Panel t	X s			X		X		X		X		X u	
LDH t	X s			X		X		X		X		X u	
Urinalysis t	X s					X v						X u	
T3 (or FT3 per local standard), FT4 and TSH t	X s				X			X w				X u	
Viscosity t	X s												
Quantitative Serum Immunoglobulin	X s			X		X		X					
Serum protein electrophoresis and serum immunofixation	X s			X		X		X					
Serum free light chain assay	X s			X		X		X					
24 hr urine protein electrophoresis and urine immunofixation	X s			X		X		X					
M-protein quantitation (urine and serum)	X s			X		X		X					
β2 microglobulin	X s												
Archival Bone Marrow Biopsy Collection x	X												
Bone Marrow Biopsy & Aspirate x,y	X			X				X					

Trial Period:	Screening Phase	Treatment Cycles a								End of Treatment	Post-treatment		
		To be repeated beyond 8 cycles											
Treatment Cycle/Title:	Screening (Visit 1)	1	2	3	4	5	6	7	8	Discon	Post-Treatment Safety Follow-up Visit	Efficacy Follow-up Visits b	Survival Follow-up c
Scheduling Window (Days) d :	-28 to -1	± 3	± 3	± 3	± 3	± 3	± 3	± 3	± 3	At time of Discon	30 days post Discon (±3 days)	Every 12 weeks post Discon (±7 days)	Every 12 weeks (±7 days) or as directed by the Sponsor
Bone marrow morphology, IHC, Cytogenetics by standard karyotyping, FISH panel z,aa	X			X				X					
Laboratory Procedures/Assessments: analysis performed by central laboratory													
Correlative Studies Blood /Bone Marrow Collection x,bb	X			X				X					
Anti-pembrolizumab Antibodies cc		X cc	X cc		X cc			X cc			X cc		
Pharmacokinetics cc		X cc,dd	X cc		X cc			X cc			X cc		
Blood for Future Biomedical Research ee	X												

Abbreviations: AE=adverse event; AP=anteroposterior; aPTT=activated partial thromboplastin time; β-HCG=beta human chorionic gonadotropin; CBC=complete blood cell count; CT=computed tomography; CTCAE=Common Terminology Criteria for Adverse Events; DNA=deoxyribonucleic acid; Discon=discontinuation; ECOG=Eastern Cooperative Oncology Group; ECI=events of clinical interest; FISH=fluorescence in situ hybridization; FT3=free triiodothyronine; FT4=free thyroxine; IHC=immunohistochemistry; INR=International Normalized Ratio; LDH=lactate dehydrogenase; MRI=magnetic resonance imaging; NCI=National Cancer Institute; PA=posterior-anterior; PD=progressive disease; PET=positron emission tomography; PK=pharmacokinetic; PT=prothrombin time; Q2W=every 2 weeks; SAE=serious adverse event; T3=triiodothyronine; TSH=thyroid stimulating hormone.

- In general, assessments/procedures are to be performed on Day 1 and prior to the first dose of treatment for each cycle unless otherwise specified. Treatment cycles are 2 weeks.
- In subjects who discontinue study therapy without documented disease progression, every effort should be made to continue monitoring their disease status every 12 weeks (±7 days) until (1) the start of new anti-cancer treatment, (2) documented disease progression, (3) death, or (4) the end of the study, whichever occurs first.
- After the start of new anti-cancer treatment or documented disease progression, the subject should be contacted by telephone approximately every 12 weeks to assess for survival status. Updated survival status may be requested by the Sponsor at any time during the course of the study. Upon Sponsor notification, all subjects who do not/will not have a scheduled study visit or study contact during the Sponsor-defined time period will be contacted for their survival status (excluding subjects who have a death event previously recorded).
- In general, the window for each visit is ± 3 days unless otherwise noted.

Trial Period:	Screening Phase	Treatment Cyclesa								End of Treatment	Post-treatment			
		To be repeated beyond 8 cycles												
Treatment Cycle/Title:	Screening (Visit 1)	1	2	3	4	5	6	7	8	Discon	Post-Treatment Safety Follow-up Visit	Efficacy Follow-up Visits b	Survival Follow-up c	
	Scheduling Window (Days) d :	-28 to -1	$\pm 3$	At time of Discon	30 days post Discon ( $\pm 3$ days)	Every 12 weeks post Discon ( $\pm 7$ days)	Every 12 weeks ( $\pm 7$ days) or as directed by the Sponsor							

e. Written consent must be obtained prior to performing any protocol specific procedure. Results of a test performed prior to the subject signing consent as part of routine clinical management are acceptable in lieu of a screening test if performed within the specified time frame (e.g., within 28 days prior to the first dose of trial treatment). Screening number will be assigned when the study informed consent is signed.
 
f. Signing the informed consent for future biomedical research (FBR) samples is optional. Detailed instructions for the collection and management of specimens for FBR are provided in the Procedures Manual and Section 12.2.
 
g. Prior medications – Record all medications taken within 28 days of screening visit. Concomitant medications – Enter new medications started during the trial through the Safety Follow-up visit. Record all medications taken for SAEs as defined in Section 7.2.
 
h. Use the International Staging System (ISS) at Screening for subject classification.
 
i. AEs and laboratory safety measurements will be graded per NCI CTCAE version 4.0. All AEs, whether gradable by CTCAE or not, will also be evaluated for seriousness.
 
j. Record all AEs occurring within 30 days after the last dose of trial treatment. Report all SAEs (related and unrelated to trial treatment) and ECIs occurring up until 90 days after the last dose of trial treatment or 30 days following cessation of treatment if the subject initiates new anticancer therapy, whichever is earlier. Afterwards, report only SAEs and ECIs that are related to trial treatment.
 
k. To be repeated every 6 cycles after cycle 6.
 
l. Vital signs to include temperature, pulse, respiratory rate, weight and blood pressure. Height will be measured at visit 1 only.
 
m. Skeletal survey should include a chest (PA or AP; lateral), skull (lateral), upper extremities (shoulder to elbow), lower extremities (hip to knee; AP), pelvis (AP), cervical/thoracic/lumbar spine (AP and lateral). A skeletal survey and/or MRI/CT/PET (MRI for subjects with bone disease and CT/PET for plasmacytomas) performed as standard of care prior to signing consent can be used for screening if performed within 28 days of Day 1. For suspected progression to bone disease bidirectional measurement of the target lytic lesions must be performed. During the course of the study or if a subject develops bone pain a skeletal survey and/or MRI/CT/PET (MRI for subjects with bone disease and CT/PET for plasmacytomas) should be performed annually or as clinically indicated. Subjects with measurable plasmacytomas at baseline should have imaging performed every 8 weeks.
 
n. Disease response assessment is based upon the multiple myeloma response criteria. Disease assessments should occur at Screening and every 4 weeks (<math>\pm 7</math> days) while on study treatment. For subjects who discontinue for reasons other than PD, assessments should continue until the subject has documented PD. Parameters assessed should include serum protein electrophoresis and serum immunofixation, serum free light chain assay, 24 hr urine protein electrophoresis and urine immunofixation, M-protein quantitation (urine and serum), and urine protein electrophoresis.
														

Trial Period:	Screening Phase	Treatment Cyclesa								End of Treatment	Post-treatment		
		To be repeated beyond 8 cycles											
Treatment Cycle/Title:	Screening (Visit 1)	1	2	3	4	5	6	7	8	Discon	Post-Treatment Safety Follow-up Visit	Efficacy Follow-up Visits b	Survival Follow-up c
	Scheduling Window (Days) d :	-28 to -1	$\pm 3$	At time of Discon	30 days post Discon ( $\pm 3$ days)	Every 12 weeks post Discon ( $\pm 7$ days)	Every 12 weeks ( $\pm 7$ days) or as directed by the Sponsor						

 
o. Subjects who have progressive disease at the Wk 12 assessment (Cycle 7) should have a confirmation assessment performed at least 28 days later (after Wk 16). Additionally, for subjects who have progressive disease at the Wk 12 assessment, a bone marrow biopsy/aspirate should be performed as part of the Wk 16 confirmation assessment. See Section 7.1.2.7.7 for additional details regarding confirmation assessments.
 
p. In subjects who discontinue study therapy without confirmed disease progression, a response assessment should be performed at the time of treatment discontinuation (i.e., date of discontinuation <math>\pm 4</math> week window). If previous assessment was performed within 4 weeks prior to the date of discontinuation, then a repeat assessment at treatment discontinuation is not mandatory.
 
q. For women of reproductive potential, a urine pregnancy test should be performed within 72 hours prior to first dose of trial treatment. If urine pregnancy results cannot be confirmed as negative, a serum pregnancy test performed by the local study site laboratory will be required. Pregnancy tests (serum and/or urine tests) should be repeated if required by local guidelines.
 
r. Coagulation factors (PT/INR and aPTT) should be tested as part of the screening procedures for all subjects. Any subject receiving anticoagulant therapy should have coagulation factors monitored closely throughout the trial.
 
s. Laboratory tests for screening are to be performed within 7 days prior to the first dose of trial treatment. See Section 7.1.3 for details regarding laboratory tests.
 
t. After Cycle 1, laboratory samples can be collected up to 72 hours prior to the scheduled time point. See Section 7.1.3 for details regarding laboratory tests. Viscosity should be performed at Screening and as clinically necessary during the trial.
 
u. Unresolved abnormal laboratory tests that are drug related AEs should be followed until resolution. Laboratory tests do not need to be repeated after the end of treatment if laboratory tests are within normal range.
 
v. To be repeated every 4 cycles after Cycle 5.
 
w. To be repeated every 3 cycles after cycle 7.
 
x. If the subject signs the Future Biomedical Research (FBR) consent, any leftover tissue that would ordinarily be discarded at the end of the main study will be retained for FBR.
 
y. Bone marrow biopsy/aspirate should be performed at Screening, Cycle 1 Day 1 (Cycle 1 Day 1 only if Screening Bone Marrow Aspirate/Biopsy was performed greater than 28 days from Day 1 Cycle 1), week 4 (<math>\pm 7</math> days), Week 12 (<math>\pm 7</math> days), to confirm sCR and CR, or as clinically indicated. For subjects who have progressive disease at the Wk 12 assessment, a bone marrow biopsy/aspirate should be performed as part of the Wk 16 confirmation assessment. A bone marrow biopsy/aspirate performed as part of standard of care prior to signing informed consent may be used for screening if performed within 28 days of Day 1. When a bone marrow biopsy is performed, the paraffin-embedded block must be sent to the central laboratory.
 
													

Trial Period:	Screening Phase	Treatment Cyclesa								End of Treatment	Post-treatment		
		To be repeated beyond 8 cycles											
Treatment Cycle/Title:	Screening (Visit 1)	1	2	3	4	5	6	7	8	Discon	Post-Treatment Safety Follow-up Visit	Efficacy Follow-up Visits b	Survival Follow-up c
	Scheduling Window (Days) d :	-28 to -1	± 3	± 3	± 3	± 3	± 3	± 3	± 3	At time of Discon	30 days post Discon (±3 days)	Every 12 weeks post Discon (±7 days)	Every 12 weeks (±7 days) or as directed by the Sponsor

z. Bone marrow morphology and IHC should be performed with each bone marrow biopsy. Cytogenetics by standard karyotyping, and FISH panel should be performed at screening only.
 
aa. FISH panel should include del 1p, del 13, del 17p13, t(4;14), t(11;14), t(14;16), and 1q21 amplification.
 
bb. Correlative study samples should be collected at Screening, at the time of the Wk 4 and Wk 12 disease response assessments, and upon progression.
 
cc. Pre-dose trough and post-dose peak PK samples will be collected at Cycles 1 and 2. Pre-dose trough samples only will be collected at Cycle 4, Cycle 7, every 6 cycles thereafter, 30 days after discontinuation of study drug, and 3 months and 6 months after discontinuation of study drug (or until the subject starts new anti-cancer therapy). All trough samples should be drawn within 24 hours before infusion of pembrolizumab. All peak samples should be drawn within 30 minutes after the end of the infusion. Anti-pembrolizumab antibodies should be drawn with all pre-dose trough PK samples, 30 days after discontinuation of study drug or until the subject starts new anti-cancer therapy. Procedures for sample collection are described in the Procedures Manual.
 
dd. An additional single PK sample should be drawn between 24 to 96 hours after Cycle 1 dosing.
 
ee. Informed consent for future biomedical research samples must be obtained before the DNA sample. DNA sample for analysis should be obtained predose, on Day 1 (or with the next scheduled blood draw) as the last sample drawn or at a later date as soon as the informed consent is obtained. Detailed instructions for the collection and management of specimens for FBR are provided in the Procedures Manual and Section 12.2.
 
Note: Cohort 2 has completed enrollment and there will be no further enrollment of subjects. All subjects in Cohort 2 have previously discontinued study treatment and must transition into long-term safety and survival follow-up.
													

**6.3 Study Flow Chart C: Cohort 3, 4A, & 4B-Hodgkin Lymphoma, Mediastinal Large B-Cell Lymphoma, & any-other PD-L1 Positive Non-Hodgkin Lymphoma (Subjects allocated to 10mg/kg Q2W).**

Trial Period:	Screening Phase	Treatment Cycles a								End of Treatment	Post-treatment		
		1	2	3	4	5	6	7	8		Post-Treatment Safety Follow-up Visit	Efficacy Follow-up Visits b	Survival Follow-up c
Treatment Cycle/Title:	Screening (Visit 1)									Discon			
Scheduling Window (Days) d :	-28 to -1	± 3	± 3	± 3	± 3	± 3	± 3	± 3	± 3	At time of Discon	30 days post Discon (±3 days)	Every 8 weeks post Discon (±7 days)	Every 12 weeks (±7 days) or as directed by the Sponsor
Administrative Procedures													
Pre-screening Informed Consent	X e												
Informed Consent	X f												
Informed Consent for Future Biomedical Research g	X												
Inclusion/Exclusion Criteria	X												
Subject Identification Card	X												
Demographics and Medical History	X												
Prior and Concomitant Medication Review h	X	X	X	X	X	X	X	X	X	X			
Trial Treatment Administration		X	X	X	X	X	X	X	X				
Post-study anticancer therapy status											X	X	
Survival Status													X
Clinical Procedures/Assessments													
Review Adverse Events i	X	X	X	X	X	X	X	X	X	X j	X		
Full Physical Examination	X			X			X k			X			
Directed Physical Examination				X			X						
Vital Signs and Weight l	X	X	X	X	X	X	X	X	X				
12-Lead Electrocardiogram	X												

Trial Period:	Screening Phase	Treatment Cycles a								End of Treatment	Post-treatment		
		To be repeated beyond 8 cycles									Post-Treatment Safety Follow-up Visit	Efficacy Follow-up Visits b	Survival Follow-up c
Treatment Cycle/Title:	Screening (Visit 1)	1	2	3	4	5	6	7	8	Discon			
Scheduling Window (Days) d :	-28 to -1	± 3	± 3	± 3	± 3	± 3	± 3	± 3	± 3	At time of Discon	30 days post Discon (±3 days)	Every 8 weeks post Discon (±7 days)	Every 12 weeks (±7 days) or as directed by the Sponsor
ECOG Performance Status	X	X	X	X	X	X	X	X	X	X			
Pulmonary Function Test m	X												
Neck, Chest, Abdominal, Pelvic PET/CT n	X				X n			X o		X p		X b	
Disease Response Assessment by Revised Response Criteria for Malignant Lymphoma					X n			X		X		X	
Assessment of Lymphoma B Symptoms n	X				X n			X		X		X	
Laboratory Procedures/Assessments: analysis performed by local laboratory													
Pregnancy Test – Urine or Serum β-HCG q	X												
PT/INR and aPTT r	X s												
CBC with Differential t	X s			X		X		X		X	X u		
Comprehensive Chemistry Panel t	X s			X		X		X		X	X u		
LDH t	X s			X		X		X		X	X u		
Urinalysis t	X s					X v					X u		
T3 (or FT3 per local standard), FT4 and TSH t	X s				X			X w			X u		
β2 microglobulin t,x	X s							X					
Bone Marrow Biopsy & Aspirate y,z	X												
Bone marrow morphology, IHC, Cytogenetics aa	X												

Trial Period:	Screening Phase	Treatment Cycles a								End of Treatment	Post-treatment		
		To be repeated beyond 8 cycles									Post-Treatment Safety Follow-up Visit	Efficacy Follow-up Visits b	Survival Follow-up c
Treatment Cycle/Title:	Screening (Visit 1)	1	2	3	4	5	6	7	8	Discon			
	Scheduling Window (Days) d :	-28 to -1	± 3	± 3	± 3	± 3	± 3	± 3	± 3	At time of Discon	30 days post Discon (±3 days)	Every 8 weeks post Discon (±7 days)	Every 12 weeks (±7 days) or as directed by the Sponsor
Laboratory Procedures/Assessments: analysis performed by central laboratory													
Archival Lymph Node Biopsy z	X												
Lymph Node Biopsy z, bb	X							X					
Correlative Studies Blood Collection z, cc	X							X					
Anti-pembrolizumab Antibodies dd		X dd	X dd		X dd			X dd			X dd		
Pharmacokinetics dd		X dd, ee	X dd		X dd			X dd			X dd		
Blood for Future Biomedical Research ff	X												

Abbreviations: AE=adverse event; aPTT=activated partial thromboplastin time; β-HCG=beta human chorionic gonadotropin; CBC=complete blood cell count; CR=complete response; CT=computed tomography; CTCAE=Common Terminology Criteria for Adverse Events; DNA=deoxyribonucleic acid; Discon=discontinuation; ECOG=Eastern Cooperative Oncology Group; ECI=events of clinical interest; FDG=fluodeoxyglucose; FEF=forced expiratory flow; FT3=free triiodothyronine; FT4=free thyroxine; FVC=forced vital capacity; HL=Hodgkin lymphoma; IHC=immunohistochemistry; INR=International Normalized Ratio; LDH=lactate dehydrogenase; MLBCL=mediastinal large B-cell lymphoma; NCI=National Cancer Institute; NHL=non-Hodgkin lymphoma; PD=progressive disease; PD-L1=programmed cell death ligand 1; PET=positron emission tomography; PK=pharmacokinetic; PT=prothrombin time; Q2W=every 2 weeks; SAE=serious adverse event; T3=triiodothyronine; TSH=thyroid stimulating hormone.

a. In general, assessments/procedures are to be performed on Day 1 and prior to the first dose of treatment for each cycle unless otherwise specified. Treatment cycles are 2 weeks.

b. In subjects who discontinue study therapy without documented disease progression, every effort should be made to continue monitoring their disease status by radiologic imaging every 8 weeks (± 7 days) until (1) the start of new anti-cancer treatment, (2) documented disease progression, (3) death, or (4) the end of the study, whichever occurs first.

- c. After the start of new anti-cancer treatment or documented disease progression, the subject should be contacted by telephone approximately every 12 weeks to assess for survival status. Updated survival status may be requested by the Sponsor at any time during the course of the study. Upon Sponsor notification, all subjects who do not/will not have a scheduled study visit or study contact during the Sponsor-defined time period will be contacted for their survival status (excluding subjects who have a death event previously recorded).
- d. In general, the window for each visit is  $\pm$  3 days unless otherwise noted.
- e. For Cohort 4B (any-other PD-L1 positive NHL) (Prior to Amendment 013-04): For subjects that have an archival biopsy sample available, pre-screening consent must be obtained prior to sending a biopsy sample to the laboratory for characterization. Subjects that do not have an archival sample available must sign the main study consent prior to undergoing a newly obtained biopsy.
